Appendix 1 – Letter of Support [redacted]

Appendix 2: Data requested and reason

Table 1: National Breast Screening Research Dataset (NBSRD) Patient Demographics data to be provided to the applicant in accordance with the cohort inclusion and exclusion criteria.

To include one row per woman included, with pseudonymised identifiers to link between tables, with ethnicity, month and year and cause of death, month and year of birth, participation in relevant research trials, and issues with data quality of NHS number.

Table 2: National Breast Screening Research Dataset (NBSRD) breast screening episode data for routine population screening episodes to be provided to the applicant in accordance with the cohort inclusion and exclusion criteria

To include one row per screening episode, with pseudonymised identifiers to link between tables, screening date, pseudonymised identifiers for the radiologists examining the mammograms, their decisions, whether the woman was recalled for further tests, whether cancer was detected.

Table 3: National Breast Screening Research Dataset (NBSRD) mammographic features to be provided to the applicant in accordance with the cohort inclusion and exclusion criteria.

Details of mammographic features associated with detected cancers. Data will be provided for screen detected breast tumours only. Features to include side of the body, mammographic characteristics such as mass or calcifications.

Table 4: National Breast Screening Research Dataset (NBSRD) cancer tumour data to be provided to the applicant in accordance with the cohort inclusion and exclusion criteria.

Tumours will be limited to C50 (breast cancer) or D05 (Breast DCIS or LCIS) records, or the pre-1995 equivalents in of '174' and '2330' respectively, only, inclusive of both screen detected and symptomatically detected breast tumours. Includes ICD classification, morphology, behaviour, grade, size, number of involved nodes, oestrogen, progesterone and HER2 status, Nottingham Prognostic Index, TNM stage, and whether screen detected.

Table 5: National Breast Screening Research Dataset (NBSRD) cancer treatment data to be provided to the applicant in accordance with the cohort inclusion and exclusion criteria.

Treatment detailed will be restricted to records for the treatment of C50 or D05, or the pre-1995 equivalents in of '174' and '2330' respectively, (inclusive of screen detected and symptomatically detected breast tumours). Includes all events those occurring within the first 365 days from DATEOFDIAGNOSISBEST. All other event dates will be excluded. Treatment includes chemotherapy, radiotherapy and surgery.

Table 6: National Breast Screening Research Dataset (NBSRD) derived ‘First Event’ data to be provided to the applicant in accordance with the cohort inclusion and exclusion criteria.

Events will be restricted to first procedure NCRAS is aware of for a C50 or D05, or the pre-1995 equivalents in of ‘174’ and ‘2330’ respectively, within the first 365 days from DATEOFDIAGNOSISBEST. All other event dates will be excluded. Datasources include registration data supplemented with SURGERYETC and OTHERPROCEDURES; HES; SACT; RTDS.

All dates and events for this table to be taken from multiple sources as described in the ‘Custom fields’ tab of the data dictionary. Includes breast surgery (breast conserving, mastectomy) underarm surgery (axillary clearance, sentinel lymph node biopsy), hormone therapy, radiotherapy, chemotherapy.

Table 7: National Breast Screening Research Dataset (NBSRD) breast screening episode data for non-routine screening episodes (high risk, GP/self-referral, non-routine recall) to be provided to the applicant in accordance with the cohort inclusion and exclusion criteria

To include date of any appointments for mammography which were not defined as screening appointments, such as GP referral.

Table 8: IMD Score – to be based upon last known address in both NCRAS and NBSS.

Index of multiple deprivation for woman’s last known address only.

Table 9: Cause of date from the civil registration mortality file.

Month and year of death and cause for main study outcome. Cause primarily to separate breast cancer death from other causes, with sensitivity analyses defining this using combinations of underlying and secondary cause. ICD10 code C50 in underlying cause is main indicator for breast cancer death. However ICD10 code C76 multiple cancers may include some breast cancer details, to check this will use ICD10 secondary cause, and refer death certificate data death cause code 1a,b,c and 2 to clarify.

Table 10 Cause of death from cancer registry

Month year and cause of death from the cancer registry, to check data quality of data from civil registration mortality file (where quality may have been limited by only linking on NHS number).

Table 11 Reference table with no data to extract

Table 12

Should the analysis expand in mutual agreement between members of the study team from Public Health England and Warwick, the following variables may also be required. Tumour histories of other (non-breast) cancers in women in the included cohort (as a potential confounder to the analysis). HES data providing additional detail of the morbidity associated with overdiagnosis and overtreatment (eg cardiac toxicity) and Charleston co-morbidity index (to characterise the population affected by overdiagnosis). Endocrine treatment data (not currently available as dispensed from community pharmacy, but linkage into cancer registry underway). Description of genomic characteristics of the cancer, which alongside other characteristics such as grade and stage may be important for predicting the benefits and harms of detecting each type of cancer in the mechanism of action analysis.

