1. Breast cancer mortality, as defined by the English Cancer Registry (where the initial source is the same but linkage to NBSS data more complete as uses multiple fields rather than just NHS number) checked against cause of death from the civil registrations mortality file. These sources have limited death data pre-1997, so we will also extract deaths data from NBSS to determine whether it can provide adequate quality, and if so use pre-1997. It is a binary outcome for each woman, with different lengths of follow up. Reported as cumulative incidence over all follow-up time, with focus on 10 year and 13 year to match previous systematic reviews.
2. All-cause mortality for everyone in the included cohort. This is taken from the civil registrations mortality file, which is populated by the Office of National Statistics. It is a binary outcome for each woman, with different lengths of follow up. Reported as cumulative incidence over all follow-up time, with focus on 10 year and 13 year to match breast cancer mortality.
3. Overdiagnosis. Overdiagnosis will be inferred as any difference between the study groups in total cumulative incidence of cancer (screen and symptomatic detected) after sufficient follow-up (the compensatory drop method). Therefore the outcome measured will be difference between groups in sum of breast cancers detected at screening and symptomatically. We will carefully consider length of follow-up in interpreting results relating to overdiagnosis, as insufficient follow up results in overestimation. We will publish a full protocol detailing all analysis methods and outcomes before commencing analysis to prevent selective reporting of outcomes or other analysis elements. Reported as cumulative incidence over all follow-up time, with focus on 10 year and 13 year to match breast cancer mortality.
4. Stage shift. This is defined by variables from the English Cancer Registry, including histological grade, cancer stage, and cancer size. The proposed mechanism of action of breast screening benefit is through detection of smaller earlier stage cancers. This will be measured for a combination of screen and symptomatic cancers, where differences between exposed and unexposed represents the stage shift of exposure. [In detail TNM stage (size, nodes, distant metastases), alternative nodal count to match Z11 and POSNOC trials 1/1-2/3+, DCIS vs invasive, invasive

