We will estimate the effect of screening threshold, using instrumental variable approaches or other analyses with consideration of causal inference. The exposure or instrumental variable will be the rate of recall of the previous 5000 cases screened by the reader (or reader pair). The readers' recall rate for previous cases may be an appropriate instrumental variable to because its effect on the outcome (for the current case) is only via the readers' threshold for the current case. This assumption will be evaluated. Instrumental variable definitions will be finalised in preliminary analyses that aim to maximise their association with recall probability, in datasets from which all outcomes have been removed. At this stage we will consider different numbers of previous cases to inform the instrumental variable definition. 5000 represents the mandated minimum per year for each reader, according to English quality assurance guidelines(26) and would give a reasonably precise estimate of recall threshold (if

the reader recalled 4% of cases the 95% binomial exact CI is 3.5% to 4.6%). We know there is substantial inter-reader variability in recall threshold, and intra-reader temporal changes (changes within a single reader over time) are much smaller, justifying increasing the number of previous cases to reduce statistical variability in the instrumental variable. We will conduct sensitivity analyses to assess whether results are robust to changes in the instrumental variable definition. We have data for a full range of thresholds for every year since 1988, and therefore have sufficient data to adjust for temporal changes. We will model changes in rates of outcome with calendar time using cubic splines.

Three models will be developed for three time horizons (shown in brackets): 1: The effect of threshold at the final screening round (27 years) with adjustment for previous attendance record, so follow-up is not contaminated with screening invitations. 2: The effect of threshold in a screening round (3 years), adjusting for clustering of screening episodes within women, the women's age at screening, and previous attendance patterns, with outcomes limited to false positive recalls, interval cancers, and stage of cancer detection. 3: If feasible, the cumulative effect of threshold over all screening rounds including the woman's entire screening history and follow-up post screening (27 years)

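### The NBSS supplement for deaths before 1997 is written for breast cancer mortality but not for all-cause mortality, and no rule covers early person-time if NBSS proves inadequate

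*Protocol*

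**What the plan says.** Three places in the protocol bear on this.

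**Outcome definitions** (Work Package 2, Measuring Outcomes, Health Outcomes). Item 1 opens "Breast cancer mortality, as defined by the English Cancer Registry", with the civil registrations mortality file as the check. It then says of both: "These sources have limited death data pre-1997, so we will also extract deaths data from NBSS". NBSS deaths are to be used for that period only if their quality is judged adequate. Item 2, all-cause mortality, names the civil file and no other source. Both items are reported as cumulative incidence, with emphasis on 10 and 13 years.

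**Recall-threshold question** (Work Package 2). It lists all-cause and breast cancer mortality among its outcomes, states "We have data for a full range of thresholds for every year since 1988", and gives models 1 and 3 a 27-year horizon.

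**Appendix 2.** Table 9, the civil file, says "ICD10 code C50 in underlying cause is main indicator for breast cancer death", "with sensitivity analyses defining this using combinations of underlying and secondary cause", and adds a check of deaths coded C76. Table 10 asks for "Month year and cause of death from the cancer registry, to check data quality of data from civil registration mortality file". For tumours, Table 4 says "Tumours will be limited to C50 (breast cancer) or D05 (Breast DCIS or LCIS) records, or the pre-1995 equivalents". Tables 5 and 6 repeat the older codes. Tables 1, 9 and 10 give no older code for cause of death.

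**The concern.** Every breast cancer death is a death from some cause, so the events in item 1 should be a subset of those in item 2. The two items as written do not guarantee this. Item 1 may draw on NBSS before 1997. Item 2 may not, although item 1 has just described the civil file as limited in that period.

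Two things follow if the text is applied literally. A woman whose early death is recorded only in NBSS could be an event for breast cancer mortality while still counted as alive for all-cause mortality. A woman who died early of something else, recorded only in NBSS, would stay in the all-cause risk set with no event. If NBSS is rejected on quality grounds, the same happens for both outcomes, because no later start of follow-up or restriction of early person-time is stated.

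At stake are the absolute mortality risks after early screens, which the protocol wants to weigh against overdiagnosis and false positive recall. A lesser matter is that a breast cancer death coded in an earlier classification has no stated place in the Table 9 rule.

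**Working it through.** **1. The two mortality outcomes side by side**

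| | Breast cancer mortality (item 1) | All-cause mortality (item 2) |
|---|---|---|
| Main source | Registry, checked against civil file | Civil file |
| Pre-1997 data acknowledged as limited | Yes, for both sources | Not mentioned, though the civil file is one of the two |
| NBSS supplement | Yes, if adequate | None stated |
| Rule if NBSS is inadequate | None stated | None stated |

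Registry deaths cannot fill the gap in item 2. Appendix 3 limits Table 10 to women who appear in Table 4, that is, women with a breast tumour record. Table 1 of Appendix 2 does request month, year and cause of death for every woman, so the data for a common rule are already in the request.

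**2. Which analyses are exposed**

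- Age extension: the comparison is made within 2000-2006. Not exposed.
- Screening interval: the question does not list mortality. Not exposed.
- Recall threshold, model 2: outcomes limited to false positive recalls, interval cancers and stage. Not exposed.
- Recall threshold, model 1 (final round, 27 years) and model 3 (cumulative, if feasible): exposed for early screens.

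**3. How much of a risk window lies before 1997**

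For a screen at the start of year s and a window of h years, the share before 1997 is (1997 − s)/h.

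| Screen at start of | Years before 1997 | Share of 10 years | Share of 13 years |
|---|---|---|---|
| 1988 | 9 | 90% | 69% |
| 1990 | 7 | 70% | 54% |
| 1993 | 4 | 40% | 31% |
| 1996 | 1 | 10% | 8% |
| 1997 or later | 0 | 0% | 0% |

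**4. Illustration of size**

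The documents do not say what fraction u of pre-1997 deaths is absent from the sources used. With a constant rate, the relative understatement is share × u. For a screen at the start of 1990:

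| Assumed u | 10-year figure too low by | 13-year figure too low by |
|---|---|---|
| 5% | 0.70 × 5% = 3.5% | 0.54 × 5% = 2.7% |
| 10% | 7.0% | 5.4% |
| 25% | 17.5% | 13.5% |

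Table 1 of the protocol gives a baseline all-cause rate of 0.6050 per 100 person-years. Over 10 years that is about 6.05 per 100 women, ignoring depletion. At u = 10% the shortfall is 0.07 × 6.05 = 0.42 per 100. For breast cancer mortality, if NBSS were rejected and no other rule applied, the figures are 0.0443 × 10 = 0.443 per 100 and 0.07 × 0.443 = 0.031 per 100.

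These values of u are assumptions. Because all-cause mortality rises with age, fewer than 70% of the deaths in a 10-year window would fall in its first seven years on that account, so the constant rate tends to overstate the loss. The figures describe one early screen, not an estimate pooled over all years.

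**5. Effect on the comparison of thresholds**

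If u does not depend on recall threshold among screens of the same period, both groups lose the same fraction of early deaths. Ratios are then roughly preserved, while absolute risks and absolute differences shrink by share × u. An abrupt change in death recording may be only partly absorbed by a smooth calendar-time spline. The documents offer nothing from which to size what remains.

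**6. The coding question**

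Table 9 names C50 and C76, both as ICD-10. The sensitivity analyses change which cause-of-death field is searched and name no older code. The certificate fields are brought in to clarify C76. None of these supplies a pre-ICD-10 equivalent, whereas Tables 4 to 6 state one.

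**The case against.** The protocol discloses the pre-1997 limitation itself, makes NBSS use conditional on quality, and commits in Work Package 1 to report completeness, change over time and misclassified cause of death. Item 1 speaks of extracting deaths data in general, so leaving NBSS out of item 2 may be a drafting slip. This is a fair reading of intent. It does not change what item 2 says, and a data-quality report is not a rule for handling what it finds.

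Exposure is narrow. It reaches one model, and a second only if feasible. An instrument built on each reader's previous 5000 cases also drops some of the earliest screens. With a range of thresholds available in every year, a gap tied to calendar date should affect readers of the same period alike. This stands, and it is why the point concerns absolute risks more than the threshold contrast.

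A reader might go further and infer that breast cancer death is identified only by C50, that early deaths carry code 174, and that they are therefore counted as other causes. On a January 1990 screen that would suggest a loss of half of the 10-year breast cancer deaths (five years of ten) or 70% (seven of ten). The documents do not support this. C50 is called the main indicator, and secondary-cause analyses, the C76 check and registry cause of death stand beside it. The Table 9 rule is written for the civil file and is not applied to NBSS. The older codes are given for tumour, treatment and first-event records, and nothing states how early deaths were coded. Work Package 1 says the full variable definitions are in a separate document, where a mapping may exist. The 50% and 70% figures also require every early death to be lost.

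**Conclusion.** The point holds for the death source. The protocol calls the civil file limited before 1997, supplements it for one mortality outcome and not the other, and states no fallback for either. Followed as written in the recall-threshold mortality analyses, pre-1997 deaths can be missed for all-cause mortality, and the two outcomes can disagree on whether the same woman died. Early 10- and 13-year cumulative incidences may be understated.

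The size cannot be derived from the documents. The illustration rests on an assumed missing fraction, a constant rate and a single early screen. No bias in the threshold comparison has been shown. The absence of an older code from Table 9 is a secondary clarification, not evidence that deaths are misclassified. The age-extension and screening-interval questions are not affected.

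The protocol should be changed before the mortality outcomes are analysed, because the source rule is best fixed without sight of the results.

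**What to change.** **Main change, Health Outcomes items 1 and 2.** State one pre-1997 death source rule for both. If NBSS deaths are judged adequate, use them for both outcomes, so that every breast cancer death is also an all-cause death. If not, mortality follow-up for both begins no earlier than 1 January 1997, by delayed entry.

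Delayed entry works only if women who died unrecorded before that date do not enter as survivors. The text should therefore require evidence that a woman was alive at entry, or limit the mortality analyses to index screening rounds on or after 1 January 1997. It should also say that 10- and 13-year risks are then estimated from that later start.

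While editing item 1, reconcile its order of sources with Appendix 2. Item 1 has the registry define the outcome and the civil file check it, whereas Tables 9 and 10 have the reverse.

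**Secondary change, Appendix 2 Table 9.** Add that the older-classification equivalent of C50 is accepted for any death record coded before ICD-10, as Tables 4 to 6 already provide for tumours and treatments. If the separate variable document already contains this, a cross-reference is enough.

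**Cost.** A few sentences and one code-list entry. No new data are needed, since Appendix 2 Table 1 already requests date and cause of death for each woman. If NBSS proves inadequate, some early person-years are given up for the mortality outcomes. The documents do not say how many.

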Appendix 3 Inclusion criteria

Women need an episode record (ODR Table 2) with date of first offered appointment (DOFOA) and age at DOFOA recorded and at least 1 demographics record (ODR Table 1) in order to be selected for the ATHENA-M cohort. So the ATHENA-M proposed cohort we are currently working towards is as follows (all dates are given for main project extract, there may be an initial extract with earlier dates and a subsequent extract with updated dates):

Women invited to routine population breast cancer screening in England from screening programme inception in 1988 to December 31st 2016, who:

- (i) Were aged 47 – 73 years at their routine screening invitation*
- (ii) Have at least one demographics record, required for linking*

The inclusion criteria by table are as follows (again for the main project extract)

- *Table 1: NHS National Breast Screening Programme (Patient Demographics) NBSS data will be restricted to women meeting the inclusion criteria.*
- *Table 2: NHS National Breast Screening Programme (routine episode) data will be restricted to women in Table 1. Records with no invitation to screening will be excluded from Table 2. Table 2 will be restricted to records with date of first offered appointment either (i) null or (ii) from screening programme inception in 1988 to 31/03/2018.*
- *Table 3: NHS National Breast Screening Programme (assessment procedures - mammographic features) NBSS data will be restricted to women in Table 1 and episodes in Table 2.*
- *Table 4: Cancer Registry data will be restricted to C50x or D05x records, or the pre-1995 equivalents in of '174' and '2330' for all women identified in Table 1, irrespective of whether the tumour was screen detected, where DATEOFDIAGNOSISBEST is between 01/01/1988 and 31/12/2018.*
- *Table 5: Cancer Registry data will be restricted to events linked to the tumours identified in Table 4 and where the event occurs within the first 365 days from DATEOFDIAGNOSISBEST and the OPCS4_CODE is identified in Table 10: Reference table OPCS4_codes. All other event data will be excluded.*
- *Table 6: Cancer Registry Derived 'First Event' data restricted to first procedure of each type the Cancer Registry is aware of for a C50x or D05x or the pre-1995 equivalents in of '174' and '2330' respectively, within the first 365 days from DATEOFDIAGNOSISBEST in Table 4. All other event data will be excluded. Data sources include registration data supplemented with SURGERYETC and OTHERPROCEDURES; HES; SACT; RTDS. All dates and events for this table to be taken from multiple sources as described in the 'Custom fields' tab of the data dictionary.*
- *Table 7: NHS National Breast Screening Programme (non-routine episode) data from BS Select will be restricted to women in Table 1. Records with no invitation to screening will be excluded from Table 7. Records in Table 7 will be restricted to records with date of first offered appointment either (i) null or (ii) from screening programme inception in 1988 to 31/03/2018*
- *Table 8: IMD Score data will be based upon last known address in NBSS.*
- *Table 9: MBIS civil registration mortality data be provided for all women identified in Table 1 and recorded in MBIS as deceased, updated in 2021.*
- *Table 10: NCRAS death data to be provided for all women identified in Table 4 and recorded in NCRAS as deceased*

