We need to understand which version of breast screening offers the most benefit with the least harm. The best evidence for this would be from a Randomised Controlled Trial (RCT). However, such trials are very expensive, often do not include sufficient women, and need at least 10 years follow-up. So a trial that started recruiting now would not give answers until the year 2036. Instead, we suggest making use of the data available from offering different versions of breast screening to over 13 million women in England over the last 25 years, as a retrospective observational research study. We have carefully designed the design and analysis using methods that allow causal inference to be made from observational data.

The Research Plan

In this very large observational study we will analyse the records of women screened in England between 1990 and 2018, with follow up available as to whether they got breast cancer (from the English Cancer Registry) and whether they died (from the civil registration mortality file). We will analyse the ages and frequencies women are invited and the proportion of women we recall for further tests affects the benefits and harms of screening. These benefits and harms will include numbers of false positive recalls, overdiagnosed cases, and mortality. We will also analyse the mechanism of action for any changes, how changes to number and nature (eg histological grade and type, stage and size) of cancers detected at screening affect number and nature of cancer detected symptomatically in the years after screening, numbers overdiagnosed and life years saved. We will explore how detecting greater numbers of Ductal Carcinoma in Situ (DCIS, i.e. most common form of potential precursor of invasive breast cancer) affects the benefits and harms of screening.

Using Findings to Change NHS Practice

We will use the findings to inform the UK National Screening Committee and revision of the English quality assurance guidelines for breast cancer screening. This will depend on results, but could for example include revising the targets for proportion of women recalled, of DCIS detection rates, or level of flexibility in the screening interval target.

1. Background and Rationale

What is the problem being addressed?

We do not currently know which version of breast cancer screening gives most benefit and least harm to the women who are screened. In particular, how often should women be

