Our comparisons are between different versions of invitations to screening. We have carefully considered time varying confounding in our analysis plans. There is a potential for time varying confounding if prognostic factors for outcomes of interest influence women moving from one treatment group to another over time, and if follow-up for individual women is split between treatment groups. Our proposed analyses explicitly account for time-varying confounding and use appropriate methods to address it. Importantly, in analyses assessing the effect of extra invitations to screening or different screening intervals it is unlikely that individual women's prognostic factors directly affect receipt of invitations (they would by contrast affect uptake of invitations, which we do not propose to assess). This is because each centre sends invitations to all eligible women regardless of their personal characteristics. However, we will examine whether centre level characteristics that may be associated with prognostic factors for outcomes of interest also affect invitations to screening. We will consider a range of centre level characteristics for potential inclusion, such as index of multiple deprivation of population served, arbitration system used, centre size, quality assurance region, and quality assurance indicators.

We will use survival analyses approaches allow for different lengths of follow-up, and will adjust standard errors account for clustering by centre, reader/reader pair, and/or screening batch where appropriate. Breast cancer treatment has developed significantly and associated mortality has decreased. We will therefore adjust for calendar time, using smoothing splines, in all time-to-event analyses.

Screening programmes can exacerbate inequality by lower uptake in lower socioeconomic groups. In addition to the main analysis we will evaluate whether the outcomes from the evaluated changes to screening age of eligibility, interval and threshold differ by index of multiple deprivation (a proxy for socioeconomic status derived from the postcode of the woman's most recent address). We will present results for how each change affects overall outcomes, and by groups according to index of multiple deprivation.

Measuring Outcomes:

Intermediate outcomes

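### The tumour extract opens in 1988, the year screening opens, so breast cancers diagnosed before then are invisible and deaths from them can enter breast cancer mortality in the recall-threshold analysis

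*Protocol*

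**What the plan says.** Appendix 3 defines the cohort as "Women invited to routine population breast cancer screening in England from screening programme inception in 1988 to December 31st 2016", with two conditions: "Were aged 47 – 73 years at their routine screening invitation", and a demographics record for linkage. Earlier breast cancer is not among the exclusions.

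Table 4 of Appendix 3 supplies breast tumours for these women "where DATEOFDIAGNOSISBEST is between 01/01/1988 and 31/12/2018". Tables 5 and 6 (treatment) depend on the tumours in Table 4. The optional extra request in Appendix 2, Table 12, covers other cancers, not breast.

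Breast cancer death is specified in two ways:

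- **Civil file.** Table 9 of Appendix 3 reads "MBIS civil registration mortality data be provided for all women identified in Table 1", where Table 1 is the demographics table, so it covers women with and without a tumour record. Appendix 2 makes C50 as underlying cause the main marker, and the registry's cause of death (Table 10) a quality check on it.
- **Registry.** Health Outcome 1 under Measuring Outcomes takes the cancer registry's definition and checks it against the civil file. Appendix 3 supplies registry deaths (Table 10) only for women who appear in Table 4.

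On the recall-threshold question, Work Package 2 says "We have data for a full range of thresholds for every year since 1988" and gives models 1 and 3 a 27-year horizon.

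**The concern.** An analysis of how a screening policy affects breast cancer death should start from women without the disease at time zero. Here the data that would establish this begin on the same date as the screens. A woman invited in 1988 at age 60 could have been diagnosed in 1985 and would have no tumour record. If she dies of that cancer with C50 as underlying cause, the civil-file rule counts the death, although no reader's threshold could have altered it. If she later has a second breast tumour, it enters Table 4 looking like a first one and adds to cumulative incidence, from which overdiagnosis is inferred.

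The look-back lengthens with calendar time, so the share of such women falls as screening year rises and the case mix of early and late screens differs. A statistical analysis plan can drop early years or add an exclusion rule, but it cannot recover records that were never requested.

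**Working it through.** **1. Look-back.** Formula: screen date minus 01/01/1988 (Appendix 3, Table 4).

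| Screen date | Maximum look-back |
|---|---|
| 01/01/1988 | 0 |
| 31/12/1988 | 1.0 year |
| 01/01/1990 | 2.0 years |
| 01/01/1993 | 5.0 years |
| 01/01/1997 | 9.0 years |
| 01/01/2000 (age-extension window opens) | 12.0 years |
| 31/12/2006 (age-extension window closes) | 19.0 years |

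**2. Look-back against follow-up.** Deaths are linked to 2021 (Work Package 1; Appendix 3, Table 9). From 01/01/1988 to the end of 2021 is 34 years, so for any screen look-back plus follow-up for death is at most 34 years.

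- A full 27 years of follow-up leaves at most 34 − 27 = 7 years of look-back, that is, screens up to 1994.
- 13 years leaves at most 34 − 13 = 21 years.
- 10 years leaves at most 34 − 10 = 24 years.

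Tumours run to 31/12/2018, a span of 31 years, so a 27-year overdiagnosis estimate leaves at most 31 − 27 = 4 years. The longest-horizon estimates come from the women whose cancer history is least known.

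**3. How one woman is classified.** Take a woman diagnosed in 1985, invited in 1990, with no later breast tumour, who dies with C50 as underlying cause in 2000.

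- Civil-file rule: she is in the demographics table, so she is in Table 9 and is an event.
- Registry rule: she is not in Table 4, so not in Table 10. Her death appears only as a disagreement with the civil file.

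With a second tumour from 1988 onwards she is in Tables 4, 9 and 10, and is an event under either rule.

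**4. Which analyses are exposed.**

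- Recall-threshold models 1 and 3: long horizon, all years; exposed.
- Recall-threshold model 2: limited to false positive recalls, interval cancers and stage; no mortality.
- Age extension: mortality is an outcome, but look-back is already 12 to 19 years; less exposed.
- Interval question: lists stage, treatment morbidity and false positive recalls; no mortality.

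**5. Scale, as illustration only.** The documents give neither the proportion of early entrants with earlier breast cancer nor their death rate. Assume 0.2% to 2%, and 1% to 3% dying of it per year. Added rate x = proportion × annual death rate × 100:

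- low: 0.002 × 0.01 × 100 = 0.002 per 100 person-years
- high: 0.02 × 0.03 × 100 = 0.06 per 100 person-years

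The sample size table in Work Package 2 gives rates of 0.0443 and 0.0433 per 100 person-years, a relative difference of 0.001 / 0.0443 = 2.3%. If x is added equally to both groups:

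- low: 0.001 / (0.0443 + 0.002) = 2.2%
- high: 0.001 / (0.0443 + 0.06) = 1.0%

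The absolute difference stays at 0.001. These figures describe early screens with full capture of deaths, not the pooled analysis.

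**The case against.** Several points against this have weight.

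- **The deaths may not count.** A reader might infer from the tumour window alone that these women's deaths are certainly events. The documents do not support that: it follows from the Appendix 2 rule but not from Health Outcome 1, under which a woman with no later tumour is absent from the registry deaths. This stands, and turns part of the point into a conflict to be reconciled.
- **Such deaths are partly visible already.** A C50 death with no Table 4 tumour can be found with the data requested, and comparing the two sources is planned. This stands, though linkage failures look the same, and women with a second tumour are missed.
- **Eligibility is inferred.** Work Package 2 says "each centre sends invitations to all eligible women regardless of their personal characteristics", which does not say that women with earlier breast cancer are eligible. True, but Appendix 3 states no exclusion either.
- **The earliest screens carry less weight.** The summary says "we will analyse the records of women screened in England between 1990 and 2018", which would drop 1988 and 1989; the threshold measure needs a reader's previous 5000 cases; and death data before 1997 are described as limited. All three reduce the effect. None removes it: a 1990 screen has 2 years of look-back, and deaths from 1997 onwards in women screened early are still captured. The focus on 10 and 13 years also lets later screens contribute.
- **No confounding is shown.** A reader might infer that the effect estimates are biased by confounding, or that all three questions are compromised. Nothing in the Protocol links earlier cancer to a reader's recall rate, and calendar time is adjusted for. The supported expectation is dilution.
- **A large percentage of baseline mortality cannot be claimed.** The 0.0443 is a single figure for the dataset, while the Protocol says breast cancer mortality has fallen, so an early-cohort denominator would be larger and any share smaller.

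**Conclusion.** The point holds in a limited form. The tumour extract gives early screens little or no cancer history, nothing else requested supplies it, and later analysis choices cannot restore it. Under the civil-file rule, deaths from cancers that predate any screen enter the first primary outcome. Under the registry rule, those without a later tumour do not, and the Protocol has to say which rule governs.

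The effect falls mainly on breast cancer mortality in recall-threshold models 1 and 3, whose full 27-year follow-up rests on screens up to 1994 with under 7 years of look-back. Second tumours extend it, to a lesser degree, to overdiagnosis. The expected harm is dilution of relative effects and a case mix that shifts with calendar time; absolute differences are not diluted if the added deaths fall equally across thresholds.

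The size is not derivable from the documents. The range in step 5, a 2.3% relative difference falling to between 2.2% and 1.0%, rests wholly on assumed inputs and overstates the pooled effect, because later screens have longer look-back and early deaths are incompletely recorded.

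**What to change.** 1. Move the lower date limit of Table 4 in Appendix 3 back to the earliest breast registrations that the registry holds and can link, for use only as a flag for previous breast cancer. Exclude flagged women at time zero from the breast cancer mortality and overdiagnosis analyses.
2. Reconcile Health Outcome 1 with Appendix 2 and with Tables 9 and 10 of Appendix 3, so that one source defines breast cancer death, and state how a C50 death without a tumour record is handled.
3. If earlier registrations cannot be supplied, add two sensitivity analyses: one counting only breast cancer deaths with a Table 4 tumour diagnosed on or after time zero, and one limited to screens with a stated minimum look-back. By step 2 of the working, a minimum of more than 7 years rules out a full 27-year estimate but leaves the 10- and 13-year results feasible.

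Cost: a small data-release amendment and slightly fewer women in the early years. The Protocol already foresees further extracts and says the linkage code exists, so the added work should be modest. Whether pre-1988 registrations can be linked and released is not stated and must be asked. The first sensitivity analysis would lose some true deaths through linkage failure and would not remove women with a second tumour.
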